5. TEST ARTICLE ALLOCATION AND MASKING

5.1. Test Article Allocation

The study lenses will be worn bilaterally in a randomized fashion using a 2x2 crossover design with 2 lens types and 2 periods. At Visit 1, eligible subjects will be randomized to one of two unique lens wear sequences using a computer-generated randomization scheme provided by the study biostatistician. Permuted block randomization will be used to avoid bias in the assignment of subjects to treatment, and to enhance the validity of statistical comparisons across treatment groups. Each block will contain two different lens trial sequences. The randomization scheme will be generated using the PROC PLAN procedure from Statistical Analysis System (SAS) Software Version 9.4 or higher (SAS Institute, Cary, NC).⁷

The study site must follow the randomization scheme provided and complete enrollment per the randomization scheme and not pre-select or assign subjects. Randomization will be performed at Visit 1 prior to the first lens fitting. The following must have occurred prior to randomization:

- Informed consent must have been obtained.
- The subject must have met all eligibility criteria.
- The subject's screening and baseline information must have been collected.

When dispensing test articles, the following steps should be followed to maintain randomization codes:

1. Investigator or designee (documented on the Delegation Log) will consult the lens fitting schedule to obtain the test article assignment for that subject prior to dispensing.
2. Investigator or designee will record the subject's number on the appropriate line of the randomization (lens fitting) schedule.
3. Investigator or designee will pull the appropriate test articles from the study supply. All test articles that are opened, whether dispensed (placed/fit on eye or dispensed outside the clinical site) or not, must be recorded on the Test Article Accountability Log in the "Dispensed" section.

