4.2. Study Design Rationale

The primary objective of this study is to evaluate the clinical performance of the test lenses against predefined targets specified in the Customer Requirements Document, based on historical performance of the ACUVUE® OASYS 1-Day for Astigmatism contact lenses.⁶ While the co-primary, safety, efficacy and secondary hypotheses will be tested for the test lenses only, a two-treatment by two-period crossover design was chosen for this study. This was considered the optimal design as it will address the primary, secondary and exploratory objectives as well as provide clinical data for the control lens. The rationale for collecting data on a marketed product is to monitor the clinical performance, as the lenses for this study will be manufactured from the Flexible Manufacturing Platform (FMP), which is not the distributional line utilized for the Control lens (AO1Dfa). Moreover, this is only the second study where lenses from the FMP line are being evaluated.

Clinical Study Protocol
Johnson & Johnson Vision Care, Inc.

Though the primary hypothesis is to test only the investigational study lens, the study design is not anticipated to have an impact on subjects' visual acuity, toric lens orientation, rotational stability, lens fit or SLFs since these endpoints are objective in nature, there will be a 1-week washout period between study lenses, and different EDTRS charts will be utilized for each eye (left vs. right) to help reduce potential for optotype memorization during collection of visual acuity.

However, there is a potential risk of carryover effect in all data collected from this study design, however, this is a greater risk for subjective responses than objective ones, i.e., CLUE vision scores. If a sequence effect is observed in the statistical model, then the primary hypothesis will be tested on data from the first period only.

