4.3. Enrollment Target and Study Duration

This study will have an enrollment target of approximately 180 subjects, with a target of at least 165 to complete. The study will be conducted at up to 14 clinical sites, where the enrollment target for each site will be approximately 10 to 20 subjects. A subject will be considered enrolled upon signing of the informed consent form.

At Visit 1, eligible subjects will be randomized to one of two lens wear sequences. There will be 4 visits in total per subject; total study duration including the enrollment period is expected to be approximately 10 weeks. Subjects who are discontinued prior to the final evaluation may be replaced at the discretion of the study sponsor. The investigation will end at the time that the study data is hard locked.

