5.2. Masking

To reduce the potential for bias, this will be a single-masked trial; subjects will not be aware of the identity of the assigned lenses, however, due to the difference in appearance of the test lenses containing the [REDACTED]

Clinical Study Protocol
Johnson & Johnson Vision Care, Inc.

chromophore, it is expected that subjects will be able to visually differentiate between the test and control designs. The identity (i.e., brand and type) of the study lenses will be masked by having the blister packs labeled with the study number, lot number, sphere power, cylinder power, axis, expiration date and randomization code. Investigators, site staff and sponsor personnel (including the medical monitor) will be aware of the identity of the test and control lenses.

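### Unmasked site staff read each sequence from a schedule provided to the site, with no concealment described, so upcoming sequences may be foreseeable; the exposure is the Period 1 fallback in section 4.2

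*Combined protocol and SAP*

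**What the plan says.** Section 5.1 has the study biostatistician generate a permuted-block scheme in PROC PLAN and supplies it to the site. The investigator or a designee "will consult the lens fitting schedule to obtain the test article assignment for that subject prior to dispensing", then enters the subject's number "on the appropriate line of the randomization (lens fitting) schedule". On blocks the section says only: "Each block will contain two different lens trial sequences". It gives no block size and does not say whether blocks are formed within site.

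Two procedural safeguards are stated. One is an instruction: "The study site must follow the randomization scheme provided and complete enrollment per the randomization scheme and not pre-select or assign subjects". The other is an order of events: consent, eligibility ("The subject must have met all eligibility criteria") and screening and baseline data must all precede randomisation. Section 4.3 adds that "A subject will be considered enrolled upon signing of the informed consent form".

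Section 5.2 masks subjects only: "Investigators, site staff and sponsor personnel (including the medical monitor) will be aware of the identity of the test and control lenses".

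Section 4.2 contains the rule that gives allocation its weight here: "If a sequence effect is observed in the statistical model, then the primary hypothesis will be tested on data from the first period only". It gives no significance level for observing such an effect.

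**The concern.** The people who decide whom to approach, consent and pass as eligible are the people who consult the schedule, and they know which lens is which. Nothing described prevents them from knowing the next sequence while making those decisions. Some of the decisions involve judgement, such as whether a candidate appears willing to comply or has clinically significant dry eye.

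In a two-period crossover this usually matters little. Every completer wears the test lens, whatever the order, so a difference between the sequence groups largely cancels from the test-lens mean. The section 4.2 fallback loses that protection. On Period 1 data the test-lens mean comes from the test-first subjects alone, about half the sample. If better-scoring candidates were placed test-first, the resulting gap between sequences would make the switch more likely and would also raise the mean then compared with 62. CLUE Vision is the endpoint at stake: section 4.2 regards subjective scores as the most exposed, and this endpoint has the lowest planned power (91%).

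**Working it through.** **Inputs from the documents.** CLUE Vision threshold 62, passed if the lower limit of the 95% CI exceeds it (14.5); historical mean 67.4, SD 19.67 (Table 8); 144 subjects for 91% power (Table 9); target of 165 completers (4.3), so 165/2, about 82 per sequence.

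**The plan's own figure.** One-sample t-test, difference 67.4 − 62 = 5.4, SD 19.67, one-sided 2.5% (matching the 95% CI rule): power at 144 is 90.5%, which agrees with the stated 91%. The one-sided 5% worded in 14.2 would give 94.9%. With 82 test-first subjects only, power at one-sided 2.5% is 69%.

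**Predictability.** If the unused lines can be read, every assignment is known. If the list is hidden but blocks are of size 2 within site, the second assignment of each block is certain, and best guessing is right 0.5 × 1 + 0.5 × 0.5 = 75% of the time. Random blocks of 2, 4 and 6 reduce this to about 69%. Varying the block size therefore helps only modestly; concealing the list matters more.

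**Assumptions for the size of the effect (none from the documents).** True test-lens mean 62; between-period correlation ρ of 0.4 or 0.6; staff judgement correlated 0.5 with the subject's underlying level; in a share s of adjacent pairs the better-looking candidate goes test-first; sequence effect tested at 5%.

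*Gap between sequences.* The expected larger of two standard normal values is 0.564, so b = s × 2 × 0.564 × 0.5 × √ρ × 19.67.
- ρ = 0.4: √0.4 × 19.67 = 12.44, so b = s × 7.02, which is 2.46 at s = 0.35 and 3.51 at s = 0.50.
- ρ = 0.6: √0.6 × 19.67 = 15.24, so b = s × 8.60, which is 3.01 and 4.30.

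*Period 1 false pass, no covariate.* Test-first subjects are shifted by b/2. The standard error is 19.67/√82 = 2.17, and the false-pass rate is 1 − Φ(1.96 − (b/2)/2.17). For b = 2.46: 1 − Φ(1.39) = 8.2%. For b = 4.30: 1 − Φ(0.97) = 16.6%.

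*Chance of the switch.* A subject's mean over both periods has variance 19.67² × (1 + ρ)/2. The standard error of the sequence difference is then 2.57 (ρ = 0.4) or 2.75 (ρ = 0.6). For b = 2.46 at ρ = 0.4 the two-sided 5% test rejects about 16% of the time; for b = 4.30 at ρ = 0.6, about 35%.

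The overall rate depends on both events jointly and was simulated. Ranges span the two correlations and repeated simulation runs. The covariate columns assume a baseline score correlated 0.5 with the subject effect.

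| Pairs steered | Period 1 false pass, unadjusted | Switch triggered, unadjusted | Overall, unadjusted | Overall with covariate, judgement adds to baseline | Overall with covariate, judgement reflects baseline only |
|---|---|---|---|---|---|
| 0 | 2.5% | 5% | about 3% | about 3–4.5% | about 3–4.5% |
| 35% | 8–11% | 16–20% | about 6–9% | about 5–8% | about 3–4.5% |
| 50% | 13–17% | 28–35% | about 10–14% | about 7–11% | about 3–4.5% |

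At 20% steered, the unadjusted overall rate is 4–5%. The full crossover test, unadjusted, stays near 2.5% throughout.

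*Cross-check with the gap imposed directly* (20,000 trials, ρ 0.3–0.7, no covariate): gaps of 2, 4 and 6 points give overall false-pass rates of about 5–6%, 12% and 25–26%, with the full crossover test again near 2.5%.

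**The case against.** The strongest reply has five parts.

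1. Section 5.1 does not say that unused lines are open to view. Staff look up the assignment for one subject, and concealment could be set out in a document not supplied. This stands: foreseeability is inferred from the procedure described.
2. The block sentence also fits blocks of 4 or 6, and within-site blocking is not stated. This stands too. Certainty about every second assignment needs both size 2 and within-site blocks.
3. Safeguards exist. Consent, eligibility and baseline data come first, and several criteria are measured (lens power range, 20/30 acuity, slit-lamp grade). This narrows the room for steering. It fixes the order of events, however, and does not stop staff knowing the next sequence while they choose whom to approach and pass.
4. Section 14.5 adjusts CLUE Vision for the baseline score. This is the most important correction to the size: the covariate absorbs part of the inflation, and nearly all of it if staff know no more than the baseline score does.
5. Harm needs a chain of assumptions: foreseeable sequences, staff able to predict scores, one-directional steering across up to 14 sites, and then the switch. The primary tests concern the test lens only and every subject is scheduled to wear it, so the documents suggest no motive. Steering could also run the other way and cost power. All of this stands. It limits confidence in the size; it does not supply a concealment step.

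**Conclusion.** The point holds as a weakness in the stated allocation procedure: unmasked staff take each sequence from a schedule provided to the site, and no concealment is described. Its consequence is confined to the section 4.2 fallback. With 35–50% of pairs steered, the overall CLUE Vision false-pass rate is about 6–14% unadjusted and about 5–11% with the planned covariate, with little or no inflation if staff judgement adds nothing to the baseline score. The steering share, judgement accuracy, correlations and trigger level are all assumptions.

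Three stronger readings are tempting, and the documents do not support them.
- A reader might infer that sites can see every upcoming sequence, or that blocks are of size 2. Neither is stated.
- A reader might infer that the main crossover result is biased. It is largely protected.
- A reader might extend the figures to the other efficacy endpoints. Those models name no baseline-score covariate, but the historical margins are wide: acuity −0.115 (SD 0.0769) against 0.00, and orientation and stability 97.5% and 100% against 80%. Plausible steering would hardly change those decisions.

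**What to change.** In section 5.1, replace look-up on the schedule with release of one sequence at a time, after eligibility at step 1.13 is recorded and before lens selection at step 1.15. Sequentially numbered opaque envelopes would do this; so would the EDC system, if it supports randomisation (section 15.1 describes it for data capture only). Generate the PROC PLAN list within site with randomly varying block sizes, for example 2, 4 and 6, not disclosed to sites, and reword the block sentence to match. If concealment is already arranged elsewhere, describe it in 5.1.

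The cost is a new list, a set of envelopes or a release form, and one rewritten paragraph. An incomplete last block of 6 can leave the sequences unequal by up to three subjects at a site. No extra subjects or visits are needed.

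This does not repair section 4.2. Even with perfect concealment, the Period 1 test has a false-positive rate of about 12–15% given that a 5% sequence test has triggered it. That two-stage switch needs its own correction.

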5.2. Masking

To reduce the potential for bias, this will be a single-masked trial; subjects will not be aware of the identity of the assigned lenses, however, due to the difference in appearance of the test lenses containing the [REDACTED]

Clinical Study Protocol
Johnson & Johnson Vision Care, Inc.

chromophore, it is expected that subjects will be able to visually differentiate between the test and control designs. The identity (i.e., brand and type) of the study lenses will be masked by having the blister packs labeled with the study number, lot number, sphere power, cylinder power, axis, expiration date and randomization code. Investigators, site staff and sponsor personnel (including the medical monitor) will be aware of the identity of the test and control lenses.

5.3. Procedures for Maintaining and Breaking the Masking

The test articles mask shall not be broken unless information concerning the lens type is necessary for the urgent medical treatment of a subject. The Sponsor must be notified before the mask is broken.

6. STUDY INTERVENTION

6.1. Identity of Test Articles

The following contact lenses will be used in this study:

Table 1: Test Articles

	Test	Contro
Test Article Name	Sofi contact lens	
Design/ Description	TRA100 and TRA200 series toric contact lens with HEVL-blocking chromophore	AOID fA
Design Name	TRA1XX and TRA2XX	AOID fA
Manufacturer	Johnson & Johnson Vision Care, Inc.	
Packaging Form	Blister packaging in sterile packing solution	
Packaging Solution	Optimized Borate Buffer (OBB) solution	
Lens Material	senofilcon A (C3) with [REDACTED] chromophore	senofilcon A (C3)
Sphere Powers (DS)	-1.50 to -4.00 in 0.25 steps	
Cylinder Powers (DC)	-0.75, -1.25	
Cylinder Axes (°)	10, 80, 90, 100, 170, 180	
Nominal Water Content %	38	
Nominal Base Curve mm	8.5	
Lens Diameter (mm)	14.3	
Fiducial marks	6 and 12 o'clock fiducial lines	
Dk (Fatt method, boundary corrected, edge corrected, $\times 10^{-11}$ [cm ² /sec] [ml O ₂ / ml x mm H ₂ O at 35°C]	103	
Modality in C11 Tent Study	Daily wear	
Replacement Frequency in C11 Tent Study	Daily disposable	
[REDACTED]	[REDACTED]	[REDACTED]

In total, both test and control lenses will be available in 132 unique lens powers (11 sphere powers x 2 cylinder powers x 6 axes).

Clinical Study Protocol
Johnson & Johnson Vision Care, Inc.

For each study lens design (test and control), the total number of test lenses to be used in this study (not including lenses that are replaced due to droppage, loss or damage) is expected to be approximately 2520 lenses (target enrollment of 180 subjects x 2 eyes per subject x 7 days per wear period).

6.2. Ancillary Supplies/Products

The following solutions will be used in this study:

Table 2: Ancillary Supplies

Solution Name/Description	Non-Preserved Rewetting Droops		
	Single use Eye-Cept® Rewetting Drops	LaciPure Saline Solution	ScleralFil Preservative Free Saline Solution
Manufacturer	Optics Laboratory	Menicon	Bausch & Lomb
Preservative	None	None	None

[figure not shown]
Lens cases and fluorescein strips (either 0.6 mg or 1.0 mg) will be supplied for use as needed.

6.3. Administration of Test Articles

Test articles will be dispensed to subjects meeting all eligibility requirements, including any dispensing requirements set forth in this clinical protocol. Subjects will be dispensed an adequate supply of test articles to complete the study. Lost or damaged test articles may be replaced at the discretion of the investigator and/or the sponsor.

6.4. Packaging and Labeling

The test articles will be packaged in blisters as the primary packaging. The test article will be over-labeled to mask the subject to the identity of the lens. The sample study label is shown below:

6.5. Storage Conditions

Test articles will be maintained at ambient temperatures at the clinical site. Test articles must be kept under secure conditions.

6.6. Collection and Storage of Samples

No samples will be collected as part of the study procedures.

Clinical Study Protocol
Johnson & Johnson Vision Care, Inc.

When possible, any lens or test article associated with an Adverse Event and/or a Product Quality Complaint must be retained and stored in a glass vial with moderate solution pending directions from the sponsor for potential return to *JNC*.

6.7. Accountability of Test Articles

JNC will provide the Investigator with sufficient quantities of study articles and supplies to complete the investigation. The Investigator is asked to retain all lens shipment documentation for the test article accountability records.

Test articles must be kept in a locked storage cabinet, accessible only to those assigned by the Investigator for dispensing. The Investigator may delegate this activity to authorized study site personnel listed on the Site Delegation Log. All test articles must be accounted. This includes:

1. What was dispensed for the subject for trial fitting, to wear out of the office, or issued for the subject to replace appropriately between visits.
2. What was returned to the Investigator unused, including expired or malfunctioning product.
3. The number and reason for unplanned replacements.

The Investigator will collect all unused test articles from the subjects at the end of the subject's participation. Subject returned unused test articles must be separated from the clinical study inventory of un-dispensed test articles and must be labeled with the subject number and date of return. Following final reconciliation of test articles by the monitor, the Investigator or monitor will return all unused test articles to *JNC*.

If there is a discrepancy between the shipment documents and the contents, contact the study monitor immediately.

7. STUDY EVALUATIONS

7.1. Time and Event Schedule

Table 3: Time and Events

Visit Information	Visit 1 Screening, Baseline, Lens Fitting #1	Visit 2 Follow-up #1	Visit 3 Continuation, Lens Fitting #2	Visit 4 Follow-up #2, Final Evaluation
Time Point	Day 0	7 ± 2 days following Visit 1	7 ± 2 days following Visit 2	7 ± 2 days following Visit 3
Minimum lens wear time immediately prior to visit	Must wear habitual lenses	1 hour (study lenses)	No requirement	1 hour (study lenses)
Estimated Visit Duration	2.5 hours	1.5 hours	1.5 hours	1.5 hours
Statement of informed consent	x			
Demographics	x			
Medical history/concomitant medications	x	x	x	x
Habitual contact lens information	x			
Habitual lens wear time	x			
Eligibility at Screening	x			
Subject reported ocular symptoms	x	x	x	x
Baseline PRO questionnaire	x			
Entrance visual acuity	x	x	x	x

Clinical Study Protocol
Johnson & Johnson Vision Care, Inc.

Visit Information	Visit 1 Screening, Baseline, Lens Fitting #1	Visit 2 Follow-up #1	Visit 3 Continuance, Lens Fitting #2	Visit 4 Follow-up #2, Final Evaluation
Time Point	Day 0	7 ± 2 days following Visit 1	7 ± 2 days following Visit 2	7 ± 2 days following Visit 3
Minimum lens wear time immediately prior to visit	Must wear habitual lenses	1 hour (study lenses)	No requirement	1 hour (study lenses)
Estimated Visit Duration	2.5 hours	1.5 hours	1.5 hours	1.5 hours
Remove habitual lenses	x		x	
Subjective Sphero-Cylindrical Refraction	x			x
Slit Lamp Biomicroscopy	x	x	x	x
Eligibility at Baseline	x			
Iris color	x			
Lens Selection	x		x	
Lens insertion and timed rotation assessments	x		x	
Lens settling	x		x	
Toric fit assessment	x		x	
General fit assessment	x		x	
Spherical over-refraction	x		x	
Lens modification (if necessary)	x		x	
Post-fit PRO questionnaire	x		x	
Additional samples of toric lens orientation performed twice	x	x	x	x
Exit visual acuity	x		x	
Discontinuation criteria	x		x	
Discontinuation instructions	x		x	
Schedule next visit	x	x	x	
Wear time and compliance		x	x	x
Collect unworn lenses		x	x	x
Follow-up PRO questionnaire		x	x	x
Distance HLHC visual acuity using ETDRS charts		x		x
Toric lens orientation		x	x	x
Lens removal		x	x	x
Continuance			x	
Subject continuation status				x

7.2. Detailed Study Procedure

VISIT 1

Subjects must wear their habitual contact lenses to this visit.

Clinical Study Protocol
Johnson & Johnson Vision Care, Inc.

Visit 1: Screenimz		
Step	Procedure	Details
1.1	Statement of Info1med Consent	
Each subject must read, understand, and sign the Statement of Info1med Consent before being enrolled into the study. The Principal Investigator or his/her designee conducting the info1med consent discussion must also sign the consent form.
 
Note: The subject must be provided a signed copy of this document.

1.2	Demographics	Record the subject's year of birth, age, gender, race, and ethnicity.
1.3	Medical History and Concomitant Medications	Record the subject's medical history and concomitant medications.
1.4	Habitual Lenses	Record the subject's habitual lens type, parameters, lens care solution, wear modality, and approximate prescription date.
1.5	Habitual lens wear time.	Record the average and comfortable wear time for the subject's habitual contact lenses.
1.6	Eligibility after Screening	
All responses to Screening Inclusion Criteria questions must be answered "yes" and all responses to Exclusion Criteria must be answered "no" for the subject to be considered eligible.
 
If subject is deemed to be ineligible after screening, proceed to Final Evaluation and complete Subject Disposition. Refraction and Biomicroscopy forms do not need to be completed as part of Final Evaluation.

Visit 1: Baseline		
Step	Procedure	Details
1.7	Subject reported ocular symptoms	Record any subject reported ocular symptoms reported with regard to their habitual contact lenses.
1.8	Baseline PRO questionnaire	Ask the subject to fill out the baseline questionnaire regarding their experience with their habitual contact lenses .
1.9	Entrance visual acuity	Record the monocular distance Snellen visual acuity for each eye (OD, OS) to the nearest letter with the subject's habitual contact lens correction. Subject must continue until at least 50% of the letters on a line are read correctly.
1.10	Remove habitual lenses	The subject's habitual contact lenses will be removed and stored in a lens case, if required.

Clinical Study Protocol
Johnson & Johnson Vision Care, Inc.

CR-6521, v 3.0

■

JJVC CONFIDENTIAL

Clinical Study Protocol
Johnson & Johnson Vision Care, Inc.

Visit 1: Baseline		
Step	Procedure	Details
1.11	Subjective spherocylindrical refraction	
Conduct a full spherocylindrical bare eye subjective refraction with binocular balance and record the resultant monocular visual acuity for each eye to the nearest letter.
 
Note: The duo-chrome test should be used for refining the monocular and binocular spherical endpoints. This test will be considered to have reached the endpoint when the targets on red and green backgrounds appear to be equally sharp. However, if the subject's response changes immediately from "red" to "green" with a 0.25DS change in power, the endpoint will be the most plus power (with "red" target clearer) before this reversal.

1.12	Slit lamp biomicroscopy	
The FDA Slit Lamp Classification Scale will be used to grade findings. If any slit lamp finding is graded as 3 or worse, the visit will be discontinued; however, the subject may repeat the baseline evaluation (one time) at a later date once the condition lessens.
 
Should the clearance of the fluorescein need to be expedited, preservative-free rewetting drops or artificial tears may be instilled.

1.13	Eligibility at baseline	
All responses to Inclusion Criteria questions must be answered "yes" and all responses to Exclusion Criteria questions must be answered "no" for the subject to be considered eligible.
 
If subject is deemed to be ineligible after baseline, proceed to Final Evaluation.

1.14	Iris color	
The investigator will record the subject's iris color using the scale provided in Appendix E.

Clinical Study Protocol
Johnson & Johnson Vision Care, Inc.

--	--	--	--

Visit 1: Lens Fittin #1		
Step	Procedure	Details
1.15	Lens selection	
Assign the study lens based on the randomization scheme. Select the fitting lens powers based on the subject's refraction for each eye, with consideration of the following guidelines:
 
1. Label cylinder axis should be determined by rounding the refraction cylinder axis to the nearest 10 degrees. Axis ending in the digit '5' should be rounded towards 180 for eyes with with-the-rule astigmatism, or towards 90 for eyes with against-the-rule astigmatism (e.g., 175 should be rounded to 180, 105 should be rounded to 100).2. Cylinder power should be chosen based on the following table:

Clinical Study Protocol
Johnson & Johnson Vision Care, Inc.

Visit 1: Lens Fittin #1								
Step	Procedure	Details						
		
 
 Vertex connected cylinder power (X) within the range: (DC)	Label cylinder power to be fit (DC)	
 
 -0.625 X < -1.125	-0.75	
 
 -1.125 X < -1.625	-1.25	
 
 
3. The fitting lens spherical equivalent (SE) power (label sphere power + 1/2 of the label cylinder power) should be as close as possible to the SE of the vertex-connected refraction. If the SE of the vertex-connected refraction is exactly half of any between two label SE powers, the least minus label power should be fit first.
	Vertex connected cylinder power (X) within the range: (DC)	Label cylinder power to be fit (DC)	-0.625 X < -1.125	-0.75	-1.125 X < -1.625	-1.25
Vertex connected cylinder power (X) within the range: (DC)	Label cylinder power to be fit (DC)							
-0.625 X < -1.125	-0.75							
-1.125 X < -1.625	-1.25							
1.16	Right eye lens insertion	
Instruct the subject to insert the right-eye lens with random orientation.
 
If lens is uncomfortable, inspect for damage and remove, reinsert or replace as necessary.
						
1.17	Timed rotation assessments during settling period	
Start a stopwatch (or suitable smartphone or tablet timing app) as soon as the right lens is inserted. Record lens rotation (direction and magnitude) to the nearest degree at one (1) and three (3) minutes following insertion.
 
Note: All lenses in this study have scribe marks at the 6 o'clock position and rotation measurements are made relative to a vertical reference line.
						
1.18	Left eye lens insertion	
Instruct the subject to insert the left-eye lens with random orientation.
 
If lens is uncomfortable, inspect for damage and remove, reinsert, or replace as necessary.
						
1.19	Timed rotation assessments during settling period	
Start a stopwatch (or suitable smartphone or tablet timing app) as soon as the left lens is inserted. Record lens rotation (direction and magnitude) to the nearest degree at one (1) and three (3) minutes following insertion.
 
Note: All lenses in this study have scribe marks at the 6 o'clock position and rotation measurements are made relative to a vertical reference line.
						
1.20	Lens settling	Allow lenses to settle for a period of at least 15 minutes following left lens insertion.						

Clinical Study Protocol
Johnson & Johnson Vision Care, Inc.

Visit 1: Lens Fittin #1		
Step	Procedure	Details
1.21	Toric fit assessment	
Record for each eye:
 
 1. The rotational position to the nearest degree 2. Lens stability with blinks 3. Toric fit acceptability. The toric lens fit will be designated as 'unacceptable' if either: 
 a. The lens ABSOLUTE ROTATION is greater than 20 degrees b. The LENS STABILITY WITH BLINK is greater than 5 degrees 
If one or both lenses demonstrate an unacceptable toric fit, the subject will be discontinued (proceed to final evaluation).

1.22	General lens fit assessment	
The fitting characteristics of the lens in both eyes will be assessed using a slit lamp. Lens position (centration, limbal exposure, edge lift) and movement (primary and up gaze as well as push-up) will be assessed. Fit acceptability is defined as any lens that does not display the following general fit characteristics:
 
 • Limbal exposure (presence of clear comea) in any direction of gaze. • Edge lift. • Insufficient movement in all three movement assessments (primary gaze, up-gaze and push-up test). • Excessive movement in primary gaze. 
If the general fit is unacceptable for either eye, the subject will be discontinued (proceed to exit evaluation).

1.23	Spherical over-refraction	
Perform monocular spherical over-refraction using duo-chrome to refine the endpoint as described in step 1.11 (the final spherical endpoint may be determined binocularly).
 
The spherical over-refraction must be plano in both eyes to continue.
 
If a non-plano over-refraction is found in either eye, the lens(es) must be refit with the indicated change in sphere power. If the indicated lens power is not available for either eye (e.g., outside the available SKU range), the subject will be discontinued (proceed to final evaluation).

Clinical Study Protocol
Johnson & Johnson Vision Care, Inc.

Visit 1: Lens Fittin #1		
Step	Procedure	Details
1.24	Lens modification (if necessary)	
If modification is necessary in one or both eyes, select the reason for refitting lenses:
 
 • The settled lens rotation is such that a different cylinder axis would be more appropriate (use the LARS rule to determine the replacement lens cylinder axis) • The spherical over-refraction is not plano • Other (specify reason) 
Repeat steps 1.16 through 1.23 for one or both eyes, as appropriate. A maximum of 2 lens modifications are allowed per eye. If, for either eye, the fit is not successful after 2 modifications, the subject will be discontinued proceed to final evaluation .

1.25	Post-fit PRO questionnaire	Subjects will complete a PRO questionnaire regarding the initial comfort, vision and handling of the study lenses.
1.26	Additional sample of toric lens orientation (1)	Instruct the subject to leave the consulting room and walk around for at least 2 minutes. Upon their return, measure and record the toric lens orientation for each eye to the nearest degree.
1.27	Additional sample of toric lens orientation 2	Repeat the previous step once again.
1.28	Exit visual acuity	Record the exit monocular distance Snellen visual acuity for each eye with the subject wearing the study lenses.
1.29	Dispensing criteria	
Lenses may be dispensed if both following conditions are met:
 
 1. The monocular distance visual acuity with the study lenses is equal to or better than 20/25 in each eye. 2. The subject indicates that the comfort and vision with the study lenses is acceptable. 
If either of these conditions is not met, the subject will be discontinued proceed to exit evaluation .

1.30	Dispensing instructions	
If the study lenses are suitable for dispensing:
 
 • Instruct the subject to wear the study lenses for at least 8 hours per day (in a daily wear / daily disposable modality) on at least 5 days of the wear period. Subjects must not wear their habitual lenses at any time during the dispensing period. • Provide the subject with a copy of the Patient Instruction Guide. • Preservative-free rewetting drops are permitted, if needed. • Dispense enough lenses for the subject to complete the wear period (i.e., up to and including their scheduled follow-up visit). At the investigator's discretion, in instances where there is a high likelihood of the subject needing replacement lenses (e.g., due to subject activities, unavailability of subject or site during the wear

Clinical Study Protocol
Johnson & Johnson Vision Care, Inc.

Visit 1: Lens Fittin #1		
Step	Procedure	Details
		
period, high likelihood of lens tears, etc.), one additional spare pair may be dispensed.
 
In the event that a subject requires additional lenses due to loss or damage, they may return to the clinical site for lens replacement. As much as reasonably possible, damaged lenses and packaging should be returned to the clinical site (in solution, if possible) for shipping to the Sponsor. If lens damage is present, complete the Product Quality Complaint Form, store the lens in a labeled vial with saline and return it to the Sponsor.
 
 • Ensure the subject is aware of the correct lens power for each eye (label the lenses with R and L as appropriate). • Instruct the subject to bring their habitual spectacles or contact lenses to the next visit (to wear following removal of the study lenses). • Instruct the subject to also bring any unused study lenses to the next visit.
1.31	Schedule next visit	
Schedule the follow-up visit to occur in 7±2 days (counting the day of this visit as day 0, the subject may return on day 5 through 9). Ensure the subject is instructed to wear the study lenses for at least 1 hour immediately prior to attending the follow-up visit.

VISIT 2

Visit 2 will occur 5 to 9 days following Visit 1. Subjects must present to this visit wearing the study lenses in both eyes, and lenses must have been worn for at least 1 hour prior to the visit.

Subjects should bring their own habitual spectacles or contact lenses to this visit to wear following study lens removal.

Visit 2: Follow-U #1		
Step	Procedure	Details
2.1	Wear time and compliance	Record the subject's wearing time and comfortable wearing time. Subjects must have worn lenses for at least 8 hours on at least 5 days during the dispensing period, and for at least 1 hour prior to attending this visit.
2.2	Collect unused lenses	Collect any unused study lenses that were dispensed at the previous visit.
2.3	Review medical history and concomitant medications	Record any changes to the subject's medical history (including adverse events) or concomitant medications.
2.4	Subject reported ocular symptoms	Record any subject reported ocular symptoms in response to a verbal open-ended symptoms questionnaire.

Clinical Study Protocol
Johnson & Johnson Vision Care, Inc.

Visit 2: Follow-U #1																	
Step	Procedure	Details															
2.5	Follow-up PRO questionnaire	
Subjects will complete a PRO questionnaire to assess their experience with the study lenses.
 
Note: at the end of the second wear period (Visit 4: Follow-up #2) the PRO questionnaire will also include questions regarding lens preference between the lenses worn in the first and second wear periods.
															
2.6	Entrance visual acuity	Record the entrance Snellen VA for each eye while wearing the study lenses.															
2.7	Distance ETDRS visual acuity	
Measure monocular distance high luminance high contrast (HLHC) visual acuity using ETDRS charts at 4 meters.
 
Measure each eye using the charts shown in the table below:
 
  
 Condition	HLHC	
   
 Room illumination	> 400 lux	
 
 Chart luminance	120 - 200 cd/m²	
 
 Eye	OD	OS	
 
 Charts	HC-1 HC-2	HC-3 HC-4	
  
 
Recorded letter-b-letter results into EDC.
	Condition	HLHC		Room illumination	> 400 lux		Chart luminance	120 - 200 cd/m ²		Eye	OD	OS	Charts	HC-1 HC-2	HC-3 HC-4
Condition	HLHC																
Room illumination	> 400 lux																
Chart luminance	120 - 200 cd/m ²																
Eye	OD	OS															
Charts	HC-1 HC-2	HC-3 HC-4															
2.8	Toric lens orientation	Record the toric lens orientation for each eye to the nearest degree.															
